5.6. Use of Center for Magnetic Resonance Research: N/A

**6. Data and Specimen Banking** N/A

**7. Sharing of Results with Participants** N/A

**8. Study Population**

8.1. Inclusion Criteria: The target population of the study includes patients needing endodontic treatment in the University of Minnesota Graduate Endodontics clinic, ages 18+. Those with an apical diagnosis of symptomatic apical periodontitis. Vulnerable populations that will be

included in the study are members of the military and those individuals from an undervalued or disenfranchised social group.

- 8.2. Exclusion Criteria: Patients with teeth that have root apices in the maxillary sinus, teeth with immature root apices, and teeth with insufficient coronal tooth structure will be excluded. For the purposes of this study children, pregnant women, prisoners, and adults lacking the capacity to consent will be excluded.
- 8.3. Screening: Screening will be completed during the participant's consultation appointment for endodontic treatment.

## 9. Vulnerable Populations

- 9.1. Vulnerable Populations:

- Children
- Pregnant women/Fetuses/Neonates
- Prisoners
- Adults lacking capacity to consent and/or adults with diminished capacity to consent, including, but not limited to, those with acute medical conditions, psychiatric disorders, neurologic disorders, developmental disorders, and behavioral disorders
- Approached for participation in research during a stressful situation such as emergency room setting, childbirth (labor), etc.
- Disadvantaged in the distribution of social goods and services such as income, housing, or healthcare
- Serious health condition for which there are no satisfactory standard treatments
- Fear of negative consequences for not participating in the research (e.g. institutionalization, deportation, disclosure of stigmatizing behavior)
- Any other circumstance/dynamic that could increase vulnerability to coercion or exploitation that might influence consent to research or decision to continue in research
- Undervalued or disenfranchised social group
- Members of the military
- Non-English speakers
- Those unable to read (illiterate)
- Employees of the researcher
- Students of the researcher
- None of the above

- 9.2. Additional Safeguards: Inclusion of these selected groups does not represent any additional safety issues. There would be no medical or dental safety issue that would warrant their exclusion. The safeguard in place to protect

their rights includes nondiscriminatory practices and equal presentation of study participation and treatment options.

## 10. Local Number of Participants

10.1. Local Number of Participants to be Consented: The approximate number of participants requested is 150. 34, or 17 per treatment group, is the lowest number that will give an 80% power to detect a mean difference between the two groups of 1 standard deviation. ([name] and [name] will each analyze a subcategory of symptomatic patients: Necrotic symptomatic teeth or Vital symptomatic teeth). Requesting 150 participants allows for greater clinical meaningfulness and accounts for possible dropouts. Randomization order for each arm of the study will be 1 to 1.

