Local Sample Size (number of participants recruited locally)	Approximately 150 participants will be recruited. [name] original study was approved for 50 pts, our study will break symptomatic patients into 1 of 2 symptomatic categories: necrotic or vital pulps. So 50 participants in each group, 100 total new patients will be recruited.

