Traditionally, the standard protocol for cleaning and shaping is completed using hand or rotary files. Various file systems are used to prepare root canal systems to the parameters set by Schilder's and Peters' principles. In addition, it is important to keep necrotic debris within the canal space as a means of preventing post-operative pain and flare-ups (3). Siqueira discovered that the factors that are commonly responsible for post-operative or interappointment pain include mechanical preparation and obturation beyond the apex, bacterial insults not present in the primary infection, and chemical extrusion of irrigant materials beyond the apex (3). Post-operative pain can occur hours to days following root canal procedures. Acute inflammation due to the aforementioned etiologic factors is the chief cause of post-operative pain. According to Gotler et al, post-operative pain typically occurs at a higher severity and incidence in vital teeth and retreatments as opposed to non-vital teeth (4). Irrigation dissolves organic material and kills microbes. It also helps prevent the binding of instruments, improves the cutting effectiveness of files, dissolves tissue, and cools the instrument and tooth (5). The most common endodontic irrigant is sodium hypochlorite (6). Sodium hypochlorite is an alkaline fluid with a pH of approximately 11-12. It hydrolyzes proteins and causes hemolysis of red blood cells which leads to the dissolution of vital, as well as necrotic tissue. Upon contact of organic debris, hypochlorous acid forms which disrupts bacterial metabolism by oxidizing the sulphydryl group of bacterial enzymes. With the use of such a caustic material, there is always the possibility of complications. Most hypochlorite accidents occur because of inaccurate working length determination, iatrogenic widening of the apical foramen, lateral perforation, or wedging of the irrigation needle. Once irrigant is extruded beyond the apex, severe pain, uncontrollable bleeding, immediate swelling, and bone and tissue necrosis can occur (7&8). Standard endodontic treatment protocol includes irrigation with 5.25% sodium hypochlorite between each file used for cleaning and shaping with a final ultrasonic activation of the sodium hypochlorite for 30 seconds per canal. Lastly, there is a one minute soak of 17% EDTA to remove the layer of debris created from cleaning and shaping (5).

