### **Inclusion criteria were:**

- (i) Patients who are 18 years of age or older
- (ii) Patients with premolar or molar with a pulpal diagnosis of necrotic pulp, symptomatic irreversible pulpitis, asymptomatic irreversible pulpitis and a periapical diagnosis designated as symptomatic including symptomatic apical periodontitis, chronic apical abscess, acute apical abscess requiring root canal therapy.
- (iii) teeth with fully formed apices
- (iv) teeth without internal or external resorption.

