accessing the pulp chamber, all caries, defective restorations, and deficient crowns were removed. A pre-endodontic build-up was placed if necessary, to maintain isolation. Straight-line access to the pulp orifices was then achieved. Hand files and an electric apex locator were used to determine the working length which was then verified with a periapical radiograph.

For the control (standard endodontic treatment) group, during the initial appointment the following were accomplished: Clinical exam, pre-endodontic build-up (if necessary), working length determination, all canals were instrumented using hand and rotary files to a minimum size and taper of at least 25/04 to within  $\frac{1}{2}$  to 1 mm short of the apical terminus. Between each file, 5.25% NaOCl was used to disinfect the canals and flush debris. Following instrumentation, NaOCl was ultrasonically activated for 30 seconds in each canal. Canals were then dried; UltraCal XS (Ultradent Products, Inc., South Jordan, UT) was placed into each canal measured 2mm short of working length. A spacer of either sterile cotton pellet or sterile sponge were placed followed by an interim restoration of either Cavit or Glass ionomer to a minimum thickness of 3.5mm.

In the experimental group during the initial appointment the following were accomplished: Clinical exam, pre-endodontic build-up (if necessary), working length determination, all canals were instrumented using hand and rotary files to a maximum size and taper of 20/07 to 1 mm short of the apical terminus. Between each file, 5.25% NaOCl was used to disinfect the canals and flush debris. Following instrumentation of the canals, Kool-dam heatless liquid dam was used to build an occlusal platform that functioned to support the GWS handpiece and seal the access opening during treatment. For molars, included gauges were used to determine the proper handpiece attachment. The GWS handpiece was positioned on the tooth for the entirety of the GWS treatment, which varied in length of time depending on the pulpal diagnosis of the tooth. The canals were then dried using paper points and UltraCal XS (Ultradent Products, Inc., South

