### **Statistical Method**

NRS pain scores were compared between treatment groups at each post-operation time point (6, 24, 72, 168 hours) using linear mixed-effects models with fixed effects for treatment, time, treatment-by-time interaction, and pre-operation NRS pain score, and a random effect for participant to account for within-participant correlation of longitudinal measurements.

Categorical NRS pain scores were compared using mixed-effects logistic regression models with fixed effects for treatment, time, treatment-by-time interaction, and pre-operation NRS pain score category, and a random effect for participant. Mechanical allodynia bite force was compared between treatment groups using the two sample t-test. Mechanical allodynia bite force was compared between treated and control teeth within each treatment group, and between visit 1 and visit 2 in treated teeth within each treatment group, using the paired t-test. Age category, sex, pulpal diagnosis, tooth type, and visit 2 NRS pain category were compared between groups using the chi-square test for association. Continuous measures are summarized using means with 95% confidence intervals. Categorical measures are summarized using rates. Analyses were conducted using R version 4.0.3.

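### The protocol announces separate analyses of necrotic and vital teeth, but neither Protocol section 15 nor the SAP provides them, and neither NRS model has a pulp term

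*Protocol*

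**What the plan says.** **Where the split is announced.** In Protocol 10.1, within the sample-size text, a parenthesis says that two investigators "will each analyze a subcategory of symptomatic patients: Necrotic symptomatic teeth or Vital symptomatic teeth". The Study Summary (Local Sample Size) says "our study will break symptomatic patients into 1 of 2 symptomatic categories: necrotic or vital pulps", then gives 50 participants in each group and 100 new patients.

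**Why pulp status matters to the outcome.** Protocol 2.3 cites a cohort study in which "post-operative pain typically occurs at a higher severity and incidence in vital teeth and retreatments as opposed to non-vital teeth". The SAP excludes previously treated teeth, so the contrast that remains relevant is vital against non-vital.

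**What the statistical sections plan.** Protocol section 15 has two-sample t-tests at 6, 24, 72 and 168 hours, a linear mixed model across time, and descriptive statistics. It does not mention pulp status.

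The SAP enrols teeth with a "pulpal diagnosis of necrotic pulp, symptomatic irreversible pulpitis, asymptomatic irreversible pulpitis" in one study. Its linear mixed NRS model has "fixed effects for treatment, time, treatment-by-time interaction, and pre-operation NRS pain score, and a random effect for participant". Its mixed logistic model has "fixed effects for treatment, time, treatment-by-time interaction, and pre-operation NRS pain score category, and a random effect for participant". Pulpal diagnosis enters the Statistical Method once: "Age category, sex, pulpal diagnosis, tooth type, and visit 2 NRS pain category were compared between groups using the chi-square test for association".

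**Treatment delivery.** In its account of the experimental group's first visit, the SAP describes the length of Gentlewave (GWS) treatment as one "which varied in length of time depending on the pulpal diagnosis of the tooth".

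**The concern.** Someone who follows the SAP exactly obtains one pooled treatment effect per time point and no effect for necrotic or for vital teeth, although the protocol sizes recruitment by these categories and assigns their analysis. The chi-square test does not fill the gap. It compares the mix of diagnoses between arms and says nothing about the treatment effect within a diagnosis.

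Two things are at stake. First, the pooled effect is an average weighted by whatever mix was enrolled, and the reader cannot see whether the two categories agree. Second, a baseline factor that the protocol itself describes as related to pain is collected and then left out of the model.

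**Working it through.** **1. The plan's own figure.** Protocol 15.2 gives 17 per group for 80% power at 1 SD. A two-sample t-test with two-sided alpha 0.05 (sidedness assumed) and the non-central t needs n = 16.7, rounded up to 17. Power is 78.1% at 16 and 80.7% at 17. The figure reproduces. Reading the Study Summary as 50 per pulp category, or 25 per arm, power within a category at 1 SD is 93%.

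**2. Tracing pulp status through the documents.**

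| Place | Use of pulp status |
|---|---|
| Protocol, Study Summary | Two categories, 50 in each |
| Protocol 2.3 | More pain in vital teeth |
| Protocol 10.1 | Each category to be analysed |
| Protocol 15 | None |
| SAP, Inclusion criteria | Both types enrolled together |
| SAP, linear mixed model | None |
| SAP, mixed logistic model | None |
| SAP, chi-square test | Distribution compared between arms |

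The announcement is not carried into any statistical section.

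**3. What the pooled effect means.** With a share w of vital teeth, the pooled effect is about w × (effect in vital) + (1 − w) × (effect in necrotic). As a deliberately extreme assumption, take 1 SD in vital and 0 in necrotic teeth. The pooled value is then 0.3, 0.5 or 0.7 SD for w = 30%, 50% or 70%. The documents give no figure for either effect or for w.

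**4. Precision of the category effects.** Assume an even split and one time point, in residual SD units. Degrees of freedom are N − 5 (four arm-by-pulp cell means and one baseline slope).

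- One category: half-width = t(0.975, N − 5) × √(1/n₁ + 1/n₂)
- Difference between categories: half-width = t(0.975, N − 5) × √(sum of the four 1/n)

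N = 38, cells 9, 10, 10, 9, t = 2.035:
- one category: 2.035 × √(1/9 + 1/10) = 2.035 × 0.459 = 0.93
- difference: 2.035 × √(2/9 + 2/10) = 2.035 × 0.650 = 1.32

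N = 100, cells of 25, t = 1.985:
- one category: 1.985 × √(2/25) = 1.985 × 0.283 = 0.56
- difference: 1.985 × √(4/25) = 1.985 × 0.400 = 0.79

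**5. Effect of adjustment on power.** The SAP linear model was simulated with 19 per arm, four complete time points, intraclass correlation 0.5, pre-operative NRS slope 0.5, half the teeth vital, and a treatment effect of 0.93 SD (the value at which 19 per arm has 80% power). All of these except the 19 per arm and the four time points are assumptions. The test is of treatment at one time point.

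| Pulp difference in pain | Without pulp | With pulp |
|---|---|---|
| None | 80.6% | 79.8% |
| 0.8 SD, none through baseline pain | 73.9% | 79.6% |
| 0.8 SD, half through baseline pain | 78.9% | 79.7% |
| 0.8 SD, all through baseline pain | 80.5% | 79.7% |

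The change runs from 79.6 − 73.9 = +5.7 points to 79.8 − 80.6 = −0.8 points. With no pulp difference, the average treatment effect from the full interaction model had about 78.0% power against 80.6%, a loss of about 2.5 points given simulation error. Type I error at a 0.8 SD pulp difference was 5.1% without and 5.0% with the pulp term.

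**The case against.** **The announcement is thin.** It is a parenthesis in a recruitment section about who handles which subcategory. The objectives, the endpoints and Protocol section 15 do not mention pulp status. This stands, and it changes where the fault lies. A reader might infer that the SAP departed from the protocol's statistical plan. It did not, because section 15 has the same gap. But the Study Summary also bases recruitment on the split, so it is more than a passing remark.

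**Randomisation protects the comparison.** This stands. A reader might infer that omitting pulp status biases the treatment effect. With 1:1 randomisation it does not, and the simulated Type I error is nominal.

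**Different treatment by category.** A reader might infer that necrotic and vital teeth received different GWS times. The SAP says only that duration depended on pulpal diagnosis. It lists three eligible diagnoses and does not say how duration maps to necrotic against vital.

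**Little power to gain, and imprecise results at 38.** Largely right. The 6-point gain needs a 0.8 SD pulp difference with none of it acting through the baseline pain already in the model. The category intervals at 38 are wide. That argues for an exploratory label, not for leaving the results out.

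**Timing and completeness.** The SAP is written in the past tense and may be an extract, so category analyses may exist elsewhere. They are absent from the documents supplied.

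**Conclusion.** The point holds as an inconsistency between what the protocol announces and what either statistical section plans. The separate necrotic and vital results are missing, and a collected prognostic factor is unadjusted.

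It does not extend to bias, nor to a shortage of patients: 50 per category would give 93% power at 1 SD. A reader might also want precision for the full 150, but nothing shows that all 150 were classified by pulp status, so only 38 and 100 are used.

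The missing category results are the main reason to act; the power argument is secondary and rests on assumed inputs. The half-widths assume an even split and would be wider for the smaller category otherwise.

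**What to change.** - **SAP, linear mixed NRS model.** Add pulp status as a fixed effect (necrotic pulp against symptomatic or asymptomatic irreversible pulpitis). From the same model with a treatment-by-pulp term, report the treatment effect with a 95% CI in necrotic and in vital teeth. If effects are given by time point, also include pulp-by-time and treatment-by-pulp-by-time.
- **Labels.** Call the category results exploratory. If outcomes have already been analysed, call the added analyses sensitivity analyses.
- **SAP, mixed logistic model.** No change is needed to the main model. A pulp term there changes the conditional odds ratio and, at 9 or 10 patients per cell, may meet sparse data, so use it at most as a sensitivity analysis.
- **Protocol section 15.** Make the matching change, so that it agrees with 10.1 and the Study Summary.

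**Cost.** Wording in two places. Adjustment adds 1 parameter to the present 9. Category effects at all four time points add 8 in total (1 + 1 + 3 + 3), making 17. Pulpal diagnosis is already recorded, so no patients, visits or data are added. If pulp status adds nothing beyond pre-operative NRS, the price is about 1 point of power for adjustment and up to about 2.5 points for the average effect from the full interaction model.

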#### **5. Procedures Involved**

- 5.1. Study Design: Patients will be asked to indicate their peak pain level in the twenty-four hours prior to the appointment using a numeric rating scale (NRS). The NRS scale will consist of a 100mm line where 0 equals 'no pain' and 100 equals the 'worst pain imaginable'. Patients will be divided into one of two treatment groups, either standard cleaning protocol or Gentlewave irrigation. Patient demographics, anesthesia, cleaning and shaping instruments, irrigation technique, and obturation method and material will be recorded, along with extent of treatment rendered, and the occurrence of over-instrumentation or overfill of obturation material.

Following the first appointment, patients will be given the same NRS assessment to take home and asked to record their level of pain at 6, 24, 72, and 168 hours post-treatment.

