## **Research Design**

This study was a single-blind, randomized, controlled clinical trial comparing the incidence and severity of postoperative pain and mechanical allodynia following root canal treatment. Based on a similar previous study (81), a sample size of 38 patients (19 per group) was necessary to achieve a power of 80%. Following a standard endodontic cleaning and shaping protocol, the independent variables are (1) conventional side-vented needles for irrigant delivery combined with ultrasonic activation and (2) irrigation using the Gentlewave system. Five 2nd year residents in the Graduate Endodontics division at the University of Minnesota School of Dentistry performed all treatments. The target population of the study included patients of the Graduate Endodontics clinic requiring root canal treatment.

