### **Exclusion criteria were:**

- (i) patients under the age of 18 or those incapable of giving informed consent
- (ii) Patient with premolar or molar with a pulpal diagnosis of normal pulp, previously treated, previously initiated and a periapical diagnosis of asymptomatic apical periodontitis or normal apical tissue requiring root canal therapy.
- (iii) teeth with immature apices

- (iv) teeth with apices in the maxillary sinus or those teeth where the apical lesion has eroded the bone of the maxillary sinus floor.
- (v) teeth with internal or external resorption,
- (vi) teeth with carious lesions or deficient crowns that cannot be repaired before accessing the pulp chamber.

Prior to treatment, a diagnostic exam and sensibility testing were performed. Pain data was collected at the time of presentation by having patients indicate their peak pain or discomfort level at the six-hour mark prior to root canal treatment and symptomatic apical periodontitis was confirmed by using percussion testing and a modified occlusal force meter (Occlusal Force-Meter, GM10, Nagaro Keiki, Tokyo, Japan), as demonstrated by Khan (75). The occlusal force meter numerical reading was recorded at maximal bite force prior to feeling pain on the symptomatic tooth and maximal bite force on the contralateral tooth. Pain measurements were made using a 0-100 NRS. The '0' mark represented 'no pain' and the '100' mark represented 'the worst pain imaginable'. There were 39 additional numeric markings between the '0' and '100' marks that patients could choose, and patients were instructed to write in their pain rating if it was not sufficiently represented on the scale. Along with the numeric scale, the surveys included Wong-Baker FACES as well as verbal markers indicating low, mild, moderate, high, and very high pain. For this study, scores in the very high range were considered severe pain. Scores 0-19 represented low pain, 20-39 was mild pain, 40-59 was moderate pain, 60-79 was high pain, and 80-100 was very high or severe pain.

Patients were divided into one of two treatment groups. Each treatment was scheduled for two appointments regardless of experimental group. For both groups, following confirmation of profound anesthesia, a rubber dam was placed in order to isolate the tooth in treatment. Prior to

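### Pulp status, which the protocol treats as prognostic for pain, is tied to neither the stated allocation rule nor the SAP's pooled models: an avoidable loss of precision and exposure to chance imbalance, not a systematic bias

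*Protocol*

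**What the plan says.** **Allocation.** Protocol section 10.1 contains the only rule: "Randomization order for each arm of the study will be 1 to 1". Section 5.1 says "Patients will be divided into one of two treatment groups, either standard cleaning protocol or Gentlewave irrigation". The SAP's Research Design section says "This study was a single-blind, randomized, controlled clinical trial", and the text after its exclusion criteria says "Patients were divided into one of two treatment groups". Neither document gives a sequence method, blocks or strata.

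**Pulp status as a prognostic factor.** Protocol section 2.3 reports from a cited cohort study that "post-operative pain typically occurs at a higher severity and incidence in vital teeth and retreatments as opposed to non-vital teeth". It gives no size for the difference.

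**Pulp status as part of the design.** The Study Summary says "our study will break symptomatic patients into 1 of 2 symptomatic categories: necrotic or vital pulps", and then "So 50 participants in each group, 100 total new patients will be recruited". Section 10.1 adds that two investigators "will each analyze a subcategory of symptomatic patients: Necrotic symptomatic teeth or Vital symptomatic teeth".

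**Analysis.** The SAP's inclusion criteria put necrotic pulps and both forms of irreversible pulpitis into one population. Under Statistical Method, the linear mixed model has treatment, time, their interaction, pre-operative NRS score and a participant effect. The mixed logistic model is the same, with the pre-operative NRS category as covariate. Pulpal diagnosis is in neither model. It appears only in a list of characteristics compared between groups by chi-square.

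**The concern.** A factor that the protocol expects to affect the outcome, and that it uses to define its sub-studies, is left to chance at allocation and is not adjusted for in the pooled analysis. It should be available in time to be used: sensibility testing is part of the diagnostic examination (Protocol section 5.2), screening is at the consultation (section 8.3), and the two procedures diverge only after working length is determined.

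The consequence depends on which analysis is run.

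- **Pooled (SAP).** If one arm happens to receive more vital teeth, part of the difference in pain between arms reflects the teeth rather than the irrigation. Variation due to pulp status also stays in the residual.
- **Separate by category (Protocol section 10.1).** Pulp status cannot confound within a category. The remaining risk is that an overall 1:1 leaves unequal arms inside a category.

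**Working it through.** **1. The plan's own figure.** Protocol section 15.2: 80% power for a difference of 1 SD, two-sample t test, alpha 0.05 (two-sided assumed). The noncentral t calculation gives n = 16.71, so 17 per group, with power 80.7%. The figure reproduces. The SAP's 19 per group comes without an effect size, so it cannot be reproduced; at 80% power it corresponds to about 0.93 SD.

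**2. Chance imbalance in the pooled analysis.** Inputs: 38 patients, 19 per arm (SAP, Research Design); 19 of 38 teeth vital (assumed, as in the protocol's plan of 50 per category). With X the number of vital teeth in one arm:

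P(X = x) = C(19, x) × C(19, 19 − x) / C(38, 19), and the arms differ by |2x − 19| vital teeth.

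- Differ by 5 or more (x ≤ 7 or x ≥ 12), that is 5/19 = 26 percentage points: 0.194.
- Differ by 7 or more (x ≤ 6 or x ≥ 13): 0.050.
- With 11 or 27 of 38 teeth vital instead, the chance of 5 or more is 0.151, so the result does not hinge on the even split.

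The same formula at the protocol's sizes, with equal arms and half the teeth vital:

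| Patients | Chance of an imbalance of 26 points or more |
|---|---|
| 38 | 19% |
| 100 | 0.9% |
| 150 | 0.1% |

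**3. What such an imbalance does.** Shift in the unadjusted arm difference = imbalance × vital effect. The documents give no vital effect; assume 10 to 20 NRS points.

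- 0.263 × 10 = 2.6 points; 0.263 × 20 = 5.3 points.
- Standard error of the arm difference = SD × √(2/19). At an assumed SD of 20 it is 6.5 points; at 30 it is 9.7 points.
- The largest ratio is 5.3/6.5 = 0.81, so the shift stays below one standard error.

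**4. What adjustment gains.** With half the teeth vital and a vital effect v, removing pulp status lowers the residual variance from SD² to SD² − v²/4. Starting from 80% power at 19 per arm, with v of 10 to 20 points and SD of 20 to 30, power rises to between 81% and 90%.

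**5. Whether the chi-square would flag it.** With diagnosis collapsed to two categories, take 12 of 19 vital in one arm and 7 of 19 in the other. Chi-square = 38 × (12 × 12 − 7 × 7)² / 19⁴ = 2.63, p = 0.10 (0.19 with continuity correction). A 26-point imbalance would not be significant, and the test corrects nothing in any case.

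**6. Arm sizes if the categories are analysed separately.**

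- 19 teeth in one category, coin-toss allocation: P(smaller arm has 6 or fewer) = 2 × P(Bin(19, 0.5) ≤ 6) = 0.167. If the overall arms are fixed at 19 each, it is 0.050 (step 2).
- 50 teeth in one category, coin toss: P(an arm below 17) = 2 × P(Bin(50, 0.5) ≤ 16) = 0.015.
- Power for 1 SD with 19 teeth is 48% at a 6/13 split and 54% at 9/10. The small category costs more than the uneven split.

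**The case against.** The strongest reply is that under randomisation an imbalance in either direction is ordinary sampling variation, already carried by the standard error and the 5% test level. That stands. A reader might infer that the treatment comparison is biased or invalid; the documents do not support this, because nothing in them favours one arm.

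Second, 38 is the number the SAP calls necessary for 80% power, not a stated enrolment, and the protocol plans 100 new patients and about 150 in all. That also stands: at those sizes a large imbalance is rare.

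Third, pre-operative NRS is in the models and may absorb part of the pulp effect. This is plausible, but the documents do not show how much, and it does not replace the diagnosis itself.

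Fourth, the rule in section 10.1 follows directly after the sentence on the two subcategories and could mean 1:1 within each. The reading is weak, since sections 12 and 13 use the word arm for treatment assignment. Still, the text is silent on strata rather than explicit that there were none, so one should not conclude that allocation was in fact unstratified.

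Fifth, the SAP is written in the past tense, so a change to the allocation may no longer be possible. That is why the model term has to be the main remedy.

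**Conclusion.** The point holds as one of precision and chance imbalance in the SAP's pooled analysis. At 19 per arm with half the teeth vital, about one allocation in five would leave the arms 5 or more vital teeth apart; at the protocol's planned size, fewer than one in a hundred would. The shift of 2.6 to 5.3 NRS points is an unadjusted figure. It rests on an assumed vital effect and is less than one standard error at the assumed SDs. It is modest, but it concerns a factor that the protocol itself names as prognostic and a diagnosis that the trial already collects.

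A reader might extend the point to the separate analyses of necrotic and vital teeth. The documents do not support that: pulp status is constant within a category, and only unequal arm sizes remain, at a small cost in power.

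**What to change.** 1. **SAP, Statistical Method (main fix).** Add pulp category (necrotic, vital) as a fixed effect in both the linear and the logistic mixed model, and state which pulpal diagnoses count as vital. Do not rely on the chi-square comparison to deal with imbalance. This works even if allocation is complete. If the categories are analysed separately, the term drops out.
2. **Protocol section 10.1.** For patients not yet allocated, state that randomisation is 1:1 within pulp category, from separate lists with randomly varying block sizes. If allocation is complete, report how it was done, including whether pulp category played a part.

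Cost: one model degree of freedom, two allocation lists instead of one, and a sentence in each document. No extra patients are needed. Blocks make upcoming assignments somewhat more predictable; varying their size limits this.
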